Nudging High Emergency Department Utilizers to Consider Non-emergent Healthcare
Resources
(NCT)

Study Protocol with Statistical Analysis Plan

January 29, 2025

Study Protocol

Background

The goal of this campaign is to reduce unnecessary emergency department (ED) visits/encourage patients who have visited a Geisinger Emergency Department four (4) or more times within the last 6 months to seek care through alternatives to ED use when appropriate. In this campaign, patients will receive outreach aligned with this goal following ED discharge and will be assigned to outreach via an interactive chatbot message or a live phone call from a Community Health Worker (CHW) or Certified Medical Assistant (CMA).

The study will assess whether ED use differs across patients in different outreach conditions.

Design

This study is a randomized controlled trial with two study arms. Patients will be randomized to receive (1) a call from a CHW or CMA or (2) a message from an interactive Artera chatbot upon ED discharge.

Methods

At the time of an eligible patient's discharge from the ED, that patient will be assigned to one of the following study arms, based on which of several ranges of randomized numbers that patient was originally assigned in their electronic chart:

1. Current standard practice (control arm): Patients in this arm will receive the current standard system outreach (i.e., call from CHW or CMA).
2. Interactive chatbot outreach (treatment arm): Patients in this arm will receive outreach from an interactive chatbot.

Power Analysis

The power calculation has been modified from the original estimation, given less-than-expected eligible patients over time. With 2,279 patients, we would have 80% power to detect a 5.0% absolute decrease in ED visits between the active arm and the control arm, with two-tailed alpha of .15, assuming a 50% baseline rate of subsequent ED visits within 120 days. The target effect size and number of patients are largely informed by practical considerations regarding the acceptable duration of the intervention (maximum of 7 months, regardless of whether the full sample is achieved), with an effect deemed useful if achieved.

Project Status

The intervention has not yet begun.

Statistical Analysis Plan

Planned Analyses

Primary Outcome: ED use [Time Frame: within 120 days following day of discharge]

Question: Does outreach decrease ED visits when including an automated text chatbot instead of live outreach?

Analysis (Confirmatory): We will test the hypothesis that outreach from an interactive chatbot versus a CHW or CMA decreases the likelihood patients will visit the ED in the 120 days following day of discharge. We will run an OLS regression including a categorical predictor variable coding for experimental arm (0 = control arm, 1 = treatment arm).

Other Pre-specified Outcomes

We will run the analysis described above on the following additional outcomes:

1. Contact with patient by monitoring center, CMA, or CHW

Contact with patient by monitoring center, CMA, or CHW (yes/no)

[Time Frame: within 3 business days following day of discharge]

2. Contact with patient by monitoring center, CMA, or CHW

Contact with patient by monitoring center, CMA, or CHW (yes/no)

[Time Frame: within 5 business days following day of discharge]

3. Time to successful contact by monitoring center, CMA, or CHW

Number of business days to successful contact by monitoring center, CMA, or CHW

4. Interaction of patient with Artera chatbot

Interaction of patient with Artera chatbot (yes/no)

[Time Frame: within 7 calendar days following first Artera outreach]

5. ED use

ED use (yes/no)

[Time Frame: within 30 days following day of discharge]

6. ED use

ED use (yes/no)

[Time Frame: within 30 days following day of outreach by Artera or CMA/CHW]

Analysis Notes

Recent work suggests that OLS regressions are appropriate in randomized experiments with binary outcome variables such as ours (Gomila, 2021).

Reference

Gomila, R. (2021). Logistic or linear? Estimating causal effects of experimental treatments on binary outcomes using regression analysis. *Journal of Experimental Psychology: General*, 150(4), 700-709. <https://doi.org/10.1037/xge0000920>

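### Does the unstated allocation ratio leave the 80% power figure for 2,279 patients in doubt?

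*Combined protocol and SAP*

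**What the plan says.** The Power Analysis gives five inputs: 2,279 patients in total, 80% power, a fall of 5.0 percentage points, a 50% baseline over 120 days, and two-tailed alpha of .15. The key sentence is "With 2,279 patients, we would have 80% power to detect a 5.0% absolute decrease in ED visits".

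On allocation, the Design section says "This study is a randomized controlled trial with two study arms". Methods adds that a patient's arm is set "based on which of several ranges of randomized numbers that patient was originally assigned in their electronic chart". The widths of the ranges, and how many belong to each arm, are not given. The document has no per-arm numbers, no allowance for loss, and no formula or software for the power calculation.

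The Power Analysis also says the calculation was revised "given less-than-expected eligible patients over time" and that the intervention will run for a "maximum of 7 months, regardless of whether the full sample is achieved".

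The SAP's confirmatory analysis is an OLS regression of the 120-day outcome on a 0/1 arm indicator.

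**The concern.** A reader who checks the figure with the default assumptions, equal arms and no loss, does not get 80%. The result is about 83%, and 80% would need only 2,076 patients, some 200 fewer than stated. That suggests an assumption that was not written down. Several ranges of chart numbers feeding only two arms also leaves room for an unequal split.

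What would be at stake is the margin. At 1:1 the trial could fall about 9% short and still have 80% power. At 35:65 it has no reserve, and at 1:2 it starts slightly below. Recruitment has already been slower than expected and the plan accepts that the sample may not be reached, so the size of the reserve is a fair question. A reader also cannot compare the final arm sizes with a planned ratio, because none is printed.

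**Working it through.** **Inputs from the Power Analysis:** N = 2,279; p1 = 0.50 (control); p2 = 0.50 − 0.05 = 0.45 (chatbot); two-sided alpha = 0.15, so z = 1.4395; 80% power, so z = 0.8416. **Assumed, because the document is silent:** the split (1:1 to 1:2, either direction), the loss (0% to 10%) and the formula (two-proportion normal approximation, pooled variance under the null).

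**Formula.** Power = Φ[(0.05 − 1.4395·SE0)/SE1], where SE0 = √{p̄(1−p̄)(1/n1 + 1/n2)}, SE1 = √{p1(1−p1)/n1 + p2(1−p2)/n2}, and p̄ is the average of p1 and p2 weighted by arm size.

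**Step 1: the plan's figure at 1:1, no loss.** n1 = n2 = 1,139.5 and p̄ = 0.475, so SE0 = 0.02092 and SE1 = 0.02089. Then (0.05 − 1.4395 × 0.02092)/0.02089 = 0.952, and power = 82.9%. Required size per arm = [1.4395·√(2 × 0.475 × 0.525) + 0.8416·√(0.25 + 0.2475)]²/0.05² = (1.0166 + 0.5936)²/0.0025 = 1,037.2, rounded up to 1,038, or 2,076 in total. The reserve is 2,279 − 2,076 = 203 patients (203/2,279 = 8.9%).

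**Step 2: does the formula matter?** At 1:1 without loss, power is 83.0% with unpooled variance, 82.9% with the arcsine method, 82.8% with a linear-model calculation (SD 0.5) and 81.8% with a continuity correction. All exceed 80%.

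**Step 3: does the split matter?** Power at N = 2,279 with no loss:

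| Split | Power | Total N for 80% |
|---|---|---|
| 1:1 | 82.9% | 2,076 |
| 40:60 | 81.7% | about 2,160 |
| 35:65 | 80.0% | about 2,280 |
| 1:2 (either direction) | 79.2-79.3% | about 2,335 |
| 1:3 | 73.7% | about 2,764 |

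From 1:1 to 1:2, power moves by 82.9 − 79.3 = 3.6 points. With a continuity correction it is 78.8% at 35:65 and 78.0% at 1:2.

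**Step 4: which assumptions return 80% with 2,279?** At 1:1 with 9% loss, 2,076/0.91 = 2,282 patients are needed, and 2,279 give 80.0%. Solving for the split with no loss gives a smaller-arm share of 35.0%. That solution is derived from the answer and has no support in the text.

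**Step 5: shortfall.** Power at 90% of the target (2,051) and at 80% (1,823):

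| Split | N = 2,051 | N = 1,823 |
|---|---|---|
| 1:1 | 79.6% | 75.8% |
| 35:65 | 76.6% | 72.6% |
| 1:2 | 75.8% | 71.8% |

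The gap between 1:1 and 1:2 stays near 4 points at each size (79.6 − 75.8 = 3.8; 75.8 − 71.8 = 4.0). At 1:1, a 20% shortfall costs 82.9 − 75.8 = 7.1 points. A large shortfall therefore matters more than the ratio, and the plan discloses that risk.

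**The case for a change.** The strongest case for a change is that allocation is a basic design fact and costs one sentence to state. Equal arms without loss do not return the stated pair, so something was left out, and at least two different designs would explain it. With alpha already at .15 and a fixed end date, a reader of a null result would want to know how much reserve the trial had. Without a printed ratio, a fault in the chart-number rule could also pass unnoticed: a final split near 800:1,479 would be expected at 35:65 but far off plan at 1:1.

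The omissions stand, and so does the arithmetic. The consequences are weaker. The 80% is not shown to be wrong; on the default reading it is met with room to spare. The 35:65 case was found by solving for 80%, so it cannot carry equal weight with 1:1, and the 800:1,479 example compares two plans that the document does not contain. Not printing the cut-offs does not show that they are unrecorded: Methods ties assignment to numbers already held in the electronic chart. Restating 80% as 83% would be right only for one ratio, no loss and an uncorrected formula, and would replace a cautious figure with a less cautious one. Power at a reduced sample would be useful to some readers, but the plan already says that size and target effect were set largely by practical limits.

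**Conclusion.** This is a small gap in reporting that an analyst fills sensibly; it is not an error in the plan. With uncorrected formulas, 2,279 patients give about 79% to 83% power for 50% against 45% at two-sided .15, for any split from 1:1 to 1:2 without loss. A continuity correction lowers that by about 1 point. The stated 80% lies inside the range and is conservative at 1:1 without loss.

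The ratio is not an input to the confirmatory analysis. A regression on a single arm indicator returns the difference between the two observed proportions whatever the arm sizes. Its precision follows from the achieved numbers, which will be known at analysis. The interval around that estimate, rather than planned power, will show what a null result can exclude.

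The conclusion assumes a split no more unequal than 1:2 and loss no greater than about 10%. With both at their limits (1:2, and 10% loss leaving 2,051 patients), power would be 75.8%. At 1:3 without loss it would be 73.7%. The document suggests neither case. No change is needed.

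### Does a two-tailed alpha of .15, stated only in the power paragraph, leave the primary test without a usable decision rule?

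*Combined protocol and SAP*

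**What the plan says.** Under Study Protocol, Power Analysis, the design figures are given together: "With 2,279 patients, we would have 80% power to detect a 5.0% absolute decrease in ED visits", and the same sentence continues "with two-tailed alpha of .15, assuming a 50% baseline rate of subsequent ED visits within 120 days". The paragraph opens by saying "The power calculation has been modified from the original estimation, given less-than-expected eligible patients over time". It closes with a rationale whose subject is effect size and sample size: "The target effect size and number of patients are largely informed by practical considerations regarding the acceptable duration of the intervention". Alpha is not mentioned in that rationale. Under Project Status the document states "The intervention has not yet begun".

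In the Statistical Analysis Plan, the primary analysis reads "Analysis (Confirmatory): We will test the hypothesis that outreach from an interactive chatbot versus a CHW or CMA decreases the likelihood", followed by "We will run an OLS regression including a categorical predictor variable coding for experimental arm". The SAP gives no significance threshold, confidence level or rule for describing a result. The Analysis Notes deal only with using OLS for a binary outcome.

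**The concern.** A two-tailed level of .15 is well above the conventional .05, and here it sits beside an analysis labelled confirmatory. If there is no effect, it allows a 15% chance of declaring some difference and a 7.5% chance (.15 / 2) of declaring a benefit. A reader of the SAP section alone would not see that error rate. The document also does not say whether .15 was in the original calculation or was relaxed when eligible patients ran short.

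The practical worry is a split result. Many readers expect a 95% confidence interval. If one is reported with a .15 test, there is a band of results that pass the test while the interval includes zero. With no written rule for that band, it could seem that the authors may choose their description once they have the data.

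**Working it through.** **Inputs.** From the Power Analysis paragraph: control rate 50%, treated rate 45% (a 5.0-point decrease), power 80%, two-tailed alpha .15, N = 2,279. The allocation ratio and any allowance for loss are not stated; I assume 1:1 and no loss, then vary both.

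**1. Is .15 a real design input or a slip?** Two-proportion normal approximation, pooled variance under the null, total N for 80% power:

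| Two-tailed alpha | N needed | Power at 2,279 |
|---|---|---|
| .05 | 3,130 | 66.7% |
| .10 | 2,466 | 77.2% |
| .15 | 2,076 | 82.9% |

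The stated 2,279 is not reproduced exactly at 1:1: 2,076 would be enough, so the plan's number errs on the safe side. With unpooled variance, n per arm = (.50 × .50 + .45 × .55) × (1.4395 + 0.8416)² / .05² = 1,035.5, so 1,036 per arm and 2,072 in total. Then 2,072 × 1.10 = 2,279.2, which fits a 10% allowance. Other unstated inputs come close too: 2:1 allocation gives 79.3% power at 2,279, and alpha of .12 at 1:1 gives 79.8%. The exact derivation stays open, but at 1:1 the two usual alternatives, .05 and .10, both need more than 2,279 patients. Nothing suggests that .15 is a typing error.

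**2. Where would test and interval disagree?** At 2,279 and 1:1, SE = √[(.2500 + .2475) / 1,139.5] = .02089.

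- Smallest decrease passing at .15 (the 85% half-width): 1.4395 × 2.089 = 3.01 points.
- Smallest decrease whose 95% interval excludes zero: 1.960 × 2.089 = 4.10 points.

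An observed decrease of 3.5 points (50.0% vs 46.5%) gives p = .094, an 85% interval of 0.5 to 6.5 and a 95% interval of -0.6 to 7.6. The 85% interval agrees with the test; only the 95% interval does not.

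**3. How often, at the plan's own effect?** Unpooled power is .830 at .15 and .667 at .05. The difference, taken before rounding, is .162, or about 16%. It is the gap between two significance standards, only one of which the plan adopts.

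**4. How firm is the band?**

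| Assumption | Band (points) |
|---|---|
| 1:1, N = 2,279 | 3.0 to 4.1 |
| 1:1, N = 2,072 | 3.2 to 4.3 |
| 1:1, N = 1,500 | 3.7 to 5.0 |
| 2:1, N = 2,279 | 3.2 to 4.3 |
| 3:1, N = 2,279 | 3.5 to 4.7 |

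The smaller samples matter because the Power Analysis paragraph caps the intervention at 7 months even if the target is not reached. At N = 2,072 and 1:1, powers of .800 and .626 put the chance of landing in the band at 17%. The band moves upward with a smaller sample or unequal allocation, but it exists in every case, because any .15 test paired with a 95% interval creates one.

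**The case for a change.** The best argument for acting is that a confirmatory claim should carry its error rate and decision rule beside the analysis, and that adding them would cost only a few sentences before outcome data exist. The shortage of eligible patients may explain .15, but the text does not say so. If the authors report a 95% interval out of habit, test and interval would disagree about one time in six at the target effect.

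Part of this stands. The document gives no reason specific to alpha, and the SAP section neither repeats .15 nor names a confidence level. Restating .15 with its matching 85% interval would be a courtesy to readers, and a 95% interval beside it is a matter of taste.

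The claim of an open decision does not stand. Protocol and SAP are one document, and .15 is attached to the same outcome, window and comparison as the primary test. A p-value of .094 is therefore significant under the plan, whatever interval is printed next to it. The 7.5% and 15% error rates are alpha restated: they would be the same with a full rationale, so they do not measure harm from its absence.

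**Conclusion.** No change to the plan is needed. The two-tailed .15 level is specified in advance on the document's own account, and applying it as written gives a primary result at a known and disclosed error rate: 15% for any false difference and 7.5% for a false benefit. Choosing a looser level when eligible patients are scarce and the intervention has a fixed maximum duration is a trade-off that the trial team may make openly. At .05 the same 2,279 patients would give only 66.7% power for 5.0 points, and 80% power would take about 3,130.

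The band of 3.0 to 4.1 points is correctly computed, but it rests on 1:1 allocation, on all 2,279 patients being analysed, and on a 95% interval that the plan does not mention. With the 85% interval that matches the test there is no disagreement. What remains is missing detail that an analyst fills by reading the power paragraph, plus a preference about reporting.

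### Minor, optional improvement: the confirmatory OLS names no baseline covariate, although the prior 6-month ED-visit count behind the eligibility rule could be pre-specified for a small gain in precision

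*Combined protocol and SAP*

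**What the plan says.** - **Model.** Under Planned Analyses, the confirmatory analysis of the primary outcome (any ED use within 120 days of discharge) is described in one sentence: "We will run an OLS regression including a categorical predictor variable coding for experimental arm", coded 0 for control and 1 for treatment. No other predictor is named there or in the Analysis Notes, which only defend OLS for a binary outcome.
- **Other outcomes.** The same model is carried over: "We will run the analysis described above on the following additional outcomes". Items 5 and 6 on that list are 30-day ED use.
- **Population.** The Background section targets "patients who have visited a Geisinger Emergency Department four (4) or more times within the last 6 months".
- **Sample size.** The Power Analysis gives 2,279 patients, 80% power, 50% versus 45%, two-tailed alpha .15. It says the calculation was revised "given less-than-expected eligible patients over time" and that the intervention has a "maximum of 7 months, regardless of whether the full sample is achieved".
- **Timing.** Project Status reads: "The intervention has not yet begun".

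**The concern.** The eligibility rule cannot be applied without looking up each patient's recent ED visits. That count is fixed before outreach, cannot be affected by the assigned arm, and measures the same behaviour as the primary outcome. It is the obvious prognostic covariate, and the model leaves it out.

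Nothing is biased by the omission. Randomization makes the unadjusted difference in proportions a valid estimate. What is lost is some precision, in a trial that is short of it: the sample was scaled back, alpha was set at .15, and enrolment stops at 7 months even if the target is missed. If more patients cannot be had, a gain that needs none is worth a few lines of text. Fixing the covariate and its form in advance also removes later discretion over adjustment.

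**Working it through.** **Inputs from the Power Analysis:** N = 2,279; control rate .50; treatment rate .45; two-sided alpha .15; power 80%.

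**Assumptions, not in the documents:** 1:1 allocation; R² of .01 to .03 between the prior count and 120-day ED use; 1,500 patients as an example of a shortfall at the 7-month cap.

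**1. The plan's own figure.** At 1:1 the standard two-proportion formula with pooled variance gives 1,038 per arm, 2,076 in total. With 2,279 patients power is about 83%, not 80%. A split near 65:35 gives 2,280 to 2,281; a 10% loss allowance at 1:1 gives 2,307. So 2,279 is not shown to be wrong, but an input is unstated. The gain is therefore computed from both starting points.

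**2. Effect of the covariate.** With n = 2,279/2 = 1,139.5 per arm,

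SE = √[(.50×.50 + .45×.55)/1,139.5 × (1 − R²)]

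Power = Φ(.05/SE − 1.440) + Φ(−.05/SE − 1.440), the second term being negligible.

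For the column anchored to the stated 80%, the unadjusted SE is .05/(1.440 + .842) = .02192, multiplied by √(1 − R²). Equivalent N is 2,279/(1 − R²).

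| R² | SE (1:1) | SE reduction | Equivalent N | Power, 1:1 | Power, anchored to 80% | Power, N = 1,500, 1:1 |
|---|---|---|---|---|---|---|
| 0 | .02089 | – | 2,279 | 83.0% | 80.0% | 69.2% |
| .01 | .02079 | 0.50% | 2,302 | 83.3% | 80.3% | 69.6% |
| .02 | .02068 | 1.01% | 2,325.5 | 83.6% | 80.6% | 69.9% |
| .03 | .02058 | 1.51% | 2,349.5 | 83.9% | 81.0% | 70.3% |

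Across these rows the gain is 0.3 to 1.0 power points.

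**3. How firm the R² range is.** An illustrative gamma-Poisson simulation, with the prior count truncated at four or more and the future visit rate scaled to 50%, gave a median R² of .020 over 16 assumed parameter sets, with a spread of .003 to .107. The spread is driven by those parameters. At 1:1 its ends give 83.1% and 86.3% power, a gain of 0.1 to 3.3 points. R² stays low because the outcome is binary and the cut at four visits restricts the covariate's range.

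**4. What it cannot do.** At alpha .05 and 1:1, unadjusted power is about 67%. To reach 80%, R² must satisfy 1 − R² = [.05/((1.960 + .842) × .02089)]² ≈ .73, so R² ≈ .27. That is well above anything in step 3.

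**The case against.** The strongest reply is that there is no defect. An unadjusted arm comparison is an accepted primary analysis of a randomized trial, and a gain of 0.3 to 1.0 power points is smaller than the 3-point gap between the stated 80% and the 83% found at 1:1. That is true, and it is why the point is minor.

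The R² range comes from assumption, and a wider slice of the same simulation gives 0.1 to 3.3 points. This stands: 0.3 to 1.0 is conditional on R² of .01 to .03 and is not a bound. The direction does not depend on it.

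The change also takes more than naming a variable. The Background does not say from which date the 6 months run, whether the current visit counts toward the four, or how a patient with repeat discharges is indexed. Because the other outcomes inherit the primary model, an amendment would also carry the covariate into the contact and chatbot items unless the text prevents it. Both points are fair, and the added wording must settle them.

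Finally, the reference to fewer eligible patients over time could suggest that accrual was already being watched. Project Status, however, states plainly that the intervention had not started. As documented, the change can still be made in advance.

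**Conclusion.** The point holds as a minor, optional improvement. The plan is valid as written. Adding the prior ED-visit count would leave the estimated risk difference the same in expectation and reduce its standard error by about 0.5% to 1.5%, equivalent to roughly 23 to 70 further patients, or 0.3 to 1.0 power points. This rests on an assumed R² of .01 to .03. The power figures use either an assumed 1:1 split or the stated 80%, and the conclusion is the same for both. Larger gains would need further prognostic covariates, and this one would not by itself justify moving to alpha .05.

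**What to change.** Before the intervention begins, amend the confirmatory analysis to:

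- regress 120-day ED use by OLS on arm plus the mean-centred log of the prior 6-month ED-visit count, with robust standard errors;
- define the count as at the index discharge, with the same look-back as the eligibility rule, stating how that discharge is identified and whether the current visit is included;
- name age or longer ED history as further covariates only if the chart holds them;
- report the unadjusted difference as a sensitivity analysis;
- apply the same covariate to the two 30-day ED outcomes (items 5 and 6), and state that items 1 to 4 keep the arm-only model.

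The core change is one or two sentences in the SAP, plus short definitions. The count used for eligibility must be kept as an analysis variable; the documents do not say whether it is stored, but it must be derivable to apply the rule. No extra patients, contacts or new measurements are needed.

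### Days to successful contact (item 3) has no value for patients never contacted and no rule for them, so the planned regression would by default compare contacted patients only

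*Combined protocol and SAP*

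**What the plan says.** The SAP, under Other Pre-specified Outcomes, lists six outcomes and states: "We will run the analysis described above on the following additional outcomes". The analysis referred to is the primary one, an OLS regression with arm (0 or 1) as its only stated predictor.

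Item 3 is titled "Time to successful contact by monitoring center, CMA, or CHW" and defined as the "Number of business days to successful contact by monitoring center, CMA, or CHW". Nothing further is said about it. Items 1 and 2 record the same kind of staff contact as yes or no, and each carries a window; item 2, for example, has "Time Frame: within 5 business days following day of discharge".

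On the arms, the primary question reads "Does outreach decrease ED visits when including an automated text chatbot instead of live outreach". The Methods section describes control outreach as a call from a CHW or CMA, and treatment outreach as the chatbot. Neither document part says what the monitoring center does in each arm, or when staff would contact a chatbot patient.

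The Analysis Notes defend OLS for binary outcomes. Item 3 is not binary.

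**The concern.** A day count to contact exists only for patients who are contacted. Because items 1 and 2 are yes/no, the plan itself allows for patients who are not. Item 3 has no rule for them, and a regression on a missing outcome drops those rows unless told otherwise.

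Contact occurs after randomization. It may differ by arm, since the control intervention is one of the contacts being counted and the treatment puts a chatbot in its place. If it does differ, the contacted patients in the two arms are not comparable groups, and the arm coefficient is no longer a randomized comparison. An arm that loses its hard-to-reach patients looks faster because the slow contacts have left the average. A reader of item 3 could then conclude that the chatbot arm was reached sooner when in fact fewer of its patients were reached.

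Even if the analyst does not accept the default, the choice of cap or coding would be made after the data are seen, and the sign of the result can depend on it.

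**Working it through.** **1. Textual check.** The time frames of the six additional outcomes are:

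| Item | Outcome | Time frame |
|---|---|---|
| 1 | Staff contact, yes/no | 3 business days from discharge |
| 2 | Staff contact, yes/no | 5 business days from discharge |
| 3 | Business days to staff contact | none |
| 4 | Chatbot interaction | 7 calendar days from first Artera outreach |
| 5 | ED use | 30 days from discharge |
| 6 | ED use | 30 days from outreach |

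Item 3 alone has none. No general missing-data rule, analysis set or censoring rule appears elsewhere.

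**2. Inputs.** The plan gives no figure for item 3, so there is none to reproduce. The only document figure used is the planned total of 2,279 (Power Analysis). Everything else is assumed:

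- Control: 40% contacted on day 1, 30% on day 5, 30% never.
- Treatment A, all late contacts lost: 40% on day 1, 60% never.
- Treatment B, half of both lost: 20% on day 1, 15% on day 5, 65% never.
- Treatment C, half of the early contacts lost: 20% on day 1, 30% on day 5, 50% never.

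**3. Formulas.** Let p be the share contacted on each day.

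- Contacted-only mean = sum(p × day) / sum(p).
- All-patient restricted mean to horizon H = sum(p × min(day, H)) + (1 − sum(p)) × H.

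**4. Means, in days.** For control, the contacted-only mean is (0.40×1 + 0.30×5)/0.70 = 1.90/0.70 = 2.71. Its restricted mean at H = 10 is 1.90 + 0.30×10 = 4.90. The other entries follow in the same way.

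| | Contacted-only | H = 5 | H = 10 | H = 20 |
|---|---|---|---|---|
| Control | 1.90/0.70 = 2.71 | 3.40 | 4.90 | 7.90 |
| A | 0.40/0.40 = 1.00 | 3.40 | 6.40 | 12.40 |
| B | 0.95/0.35 = 2.71 | 4.20 | 7.45 | 13.95 |
| C | 1.70/0.50 = 3.40 | 4.20 | 6.70 | 11.70 |

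**5. Treatment minus control, in days.**

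| | Contacted-only | H = 5 | H = 10 | H = 20 |
|---|---|---|---|---|
| A | −1.71 | 0.00 | +1.50 | +4.50 |
| B | 0.00 | +0.80 | +2.55 | +6.05 |
| C | +0.69 | +0.80 | +1.80 | +3.80 |

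At 10 days the contacted-only result is reversed in A, masked in B and attenuated in C. At 5 days, A is a spurious gap rather than a reversal.

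**6. Patients left out, assuming equal allocation.** A: 1 − (0.70 + 0.40)/2 = 45%. B: 1 − (0.70 + 0.35)/2 = 47.5%. C: 1 − (0.70 + 0.50)/2 = 40%. Multiplied by 2,279, these are about 1,026, 1,083 and 912 patients.

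**7. What items 1 and 2 would show (treatment vs control).** A: 40% vs 40% at 3 days, 40% vs 70% at 5 days. B: 20% vs 40%, then 35% vs 70%. C: 20% vs 40%, then 50% vs 70%.

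**8. Null case and opposite direction.** If treatment matches control, both measures give 0.00 at every horizon. If treatment gains contacts instead, swapping the arms flips every sign: A becomes +1.71 contacted-only against −1.50 at 10 days.

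**9. Why late contacts need the cap too.** Take A with control's late 30% on day 8 and H = 5. If only the never-contacted are set to 5, control is 0.4 + 2.4 + 1.5 = 4.30 against 3.40 for treatment. With late contacts also set to 5, both are 3.40.

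**The case against.** The plan never says that uncontacted patients are excluded. What is documented is a missing rule, and the contacted-only analysis is one way of filling it. That stands: confidence is high for the omission, while the presence, direction and size of any bias are unknown.

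The outcome is also minor. Only the 120-day ED analysis is labelled confirmatory, and no sample size or main conclusion rests on item 3. Items 1 and 2 sit directly above it and, in the illustrations, show contact gaps of 20 to 35 points at 5 days. That limits the harm but does not remove it. Those items neither define item 3 nor correct its coefficient, and in case A item 1 shows no gap.

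The all-patient benchmark moves with the horizon (in B, from +0.80 to +6.05 days), and at long horizons it largely restates the contact-rate gap: in B at 20 days it is 0.35×20 = 7.00 less 0.95, or 6.05. This is fair, and it argues for fixing one modest horizon in advance. A time-to-event analysis would also close the gap. None of these points defends a contacted-only regression.

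Finally, these patients are frequent ED users and may be discharged again before first contact. The plan does not say whether contact prompted by a later discharge counts, which the definition should settle.

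**Conclusion.** The point holds. Item 3 cannot be computed for never-contacted patients, the plan has no rule for them, and its default reading yields a comparison of subsets selected after randomization. If staff contact differs by arm, the coefficient can be attenuated, masked or reversed. The figures rest wholly on assumed contact rates and days, and the omitted counts also assume equal allocation and the full 2,279, which may not be reached within the 7-month limit. With identical contact processes there is no bias. The primary ED analysis is unaffected. This should be corrected, but it does not threaten the trial's main conclusion.

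**What to change.** Define item 3 as business days from the index discharge to first successful contact by monitoring center, CMA or CHW, up to one pre-specified horizon (10 business days, for example). Include every randomized patient. Assign the horizon value both to those never contacted and to those first contacted after it. State whether contact prompted by a later discharge counts. Report the arm difference in this restricted mean beside the contact rates from items 1 and 2. OLS can stay, since the outcome is then defined for everyone.

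The cost is a few lines of SAP text and keeping contact dates through the chosen horizon. The protocol's status section says outreach had not started, so the change can be made before any data exist.
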